#### 10.6 Key Roles and Study Governance

The clinical trial will be centrally coordinated by the Lead Investigator, [name]. Participating sites include UofSC and UoU. The Data Coordination Unit (DCU) at MUSC is a nationally renowned center that provides assistance with the design of clinical trials, analysis of clinical trial data, as well as establishing, implementing, and maintaining data and project management systems for multicenter clinical trials, administrative, and statistical support. The DCU will provide the data management backbone for this trial, including online data collection forms, data collection guidelines, continuous data surveillance, and AE reporting.

#### 10.7 Safety Oversight

A DSMB will provide the safety oversight for this trial. The DSMB meets annually to review safety data and trial progress.

#### 10.8 Clinical Monitoring

#### 10.8.1 Site Initiation Procedure

A site initiation visit by the PI and Project Manager will occur to ensure that the following steps are performed in accordance with a unified protocol: 1) participant enrollment, 2) use of the WebDCUTM system, 3) behavioral assessments, 4) intake of individual characteristics, 5) neuroimaging acquisition, and 6) speech therapy. We also implement yearly online recertification for the SLPs and trained research staff to review the SET procedures with the site SLPs and study coordinators and ensure continued proficiency of the study protocol.

#### 10.8.2 Treatment manual, on-site training and online recertifications

The SLP Manager and the Project Manager will create a manual for standard operating procedures (SOPs), and for the administration of the behavioral assessments and of SET. This manual will be shared at the initiation of the study and subsequently throughout the study. The manual and the SOPs will be reviewed through site recertifications.

The SLP Manager and the Project Manager will perform site recertifications every 6 months. This will be done separately and more frequently than site visits, and will be performed via teleconference through the MUSC's Telehealth Center. The MUSC's Telehealth Center is an initiative that supports telehealth activities in diverse applications including health care and research. The Center coordinates training in the use of telehealth technologies for each site, assists with ongoing quality maintenance, and facilitates the administrative management of telehealth activities. We will use a HIPAA-compliant virtual platform for site communication and recertifications. During the recertification process, the SLP Manager and the Project Manager will teleconference with the site study coordinator, and the site SLP and review the manual and SOPs. They will run through case scenarios to ensure understanding of the procedures and answer questions. They will also review data entry and storage compliance, whilst data management is performed independently by the MUSC DCU.

# 10.9 Data Collection and Management Responsibilities

The research team will be trained by the SLP Manager on methods for data collection. Source documents for assessments will be stored in local site's lab. Training will be provided to research team for use of WebDCUTM online data storage. The SLP Manager will do routine, periodic review of source documents and data stored on WebDCUTM to ensure proper documentation and storage of all data.

#### 10.9.1 Sharing of Results with Subjects

If there are any significant new findings during the course of the study, the participants will be notified. Participant may also request copies of assessment documentation or MRI for their own use or to provide to their primary care physicians. Informal verbal request is all that will be required to obtain documents. All assessments are de-identified as they are recorded by participant number. Each participant will receive a follow-up appointment after study completion to discuss results of study participation. This is not mandatory, but with experience from previous aphasia trials, participants typically request this meeting.

#### 10.9.2 Protocol Deviations

A Protocol Deviation is any variance from the protocol involving a subject or subjects that is not approved by the IRB prior to its initial implementation and occurs when a member of the study departs from the IRB-approved protocol in any way without the investigator first obtaining IRB approval.

What are not considered to be protocol deviations are changes or departures from the study design or procedures that are due to a study participant's non-adherence. This should not be submitted to the IRB. This should be documented in a Note to File for the participant records.

In the event of a Protocol Deviation, the research team member should contact the SLP Manager at MUSC and provide details of the deviation. The SLP Manager will then initiate the protocol deviation procedure.

## Summary of Changes

Version 5; July 2024

- Added Title Page and Summary of Changes.
- Section 7. Clarified that the analyses will adjust for the *centrally scored* baseline WAB-AQ. Updated primary analysis model to include baseline VPM as a covariate to increase efficiency.
- Section 8. Specified variables to use to define nearest neighbors for imputation of missing data.
- Section 11. Updated secondary analysis plan to mixed model approach to account for different timepoints.
- Section 15. Updated exploratory analysis plan to mixed model approach to account for different timepoints.

Version 4; September 2023

- Section 2. Updated “time from stroke onset” to “age at stroke onset” in the list of baseline variables to be compared by treatment group.
- Section 12. Added clearer language describing that the safety monitoring plan includes testing for worsening only of the primary outcome.

Version 3; June 2022

- Section 6. Changed “permuted block design” to “minimization” as minimization is more similar to the hierarchical restrictive covariate adaptive randomization procedure used in SpARc. Clarified that the randomization approach used in SpARc provides a *higher* level of allocation randomness than minimization.
- Section 7. Clarified that the primary outcome is calculated as the change in *average* VPM as VPM is measured on two tasks at each visit. Added the following sentence: “Empirical robust sandwich estimators will be used to account for the randomization procedure in order to appropriately estimate the marginal treatment effect.” Added the EMPIRICAL keyword to the PROC MIXED code. Corrected PROC MIXED syntax to include main effects for arm and visit.
- Section 11. Added individual components of the primary outcome (VPM on Narrative task and Procedural task) as secondary endpoints.
- Section 12. Added new monitoring plan for worsening in the primary outcome.

Version 2; August 2021

- Section 6. Updated the randomization procedure to be used from “asymptotic maximal procedure” to “hierarchical restrictive covariate adaptive randomization procedure” given the small sample size and number of baseline covariates.
- Section 7. Added the following sentence: “As an exploratory analysis, the combined SET duration versus control comparison will be tested at a two-sided alpha of 0.05.”
- References were deleted as the only cited reference was to the asymptotic maximal procedure.

## 1. SYNOPSIS

*Speech entrainment for Aphasia Recovery (SpARc)* is a prospective, controlled, randomized, assessor blinded, phase II clinical trial (n=80). The primary objective is to estimate the dose (duration of treatment in weeks) of SET with the highest effect size on speech fluency Verbs Per Minute (VPM) as compared to control (no SET). We will enroll 80 patients and randomly assign them 1:1:1:1 to one of the 4 groups (A, B, C, D):

- A - SET for 3 weeks (15 days, 1 hour daily, 5 x week)
- B - SET for 4.5 weeks (22 days, 1 hour daily, 5 x week)
- C - SET for 6 weeks (30 days, 1 hour daily, 5 x week)
- D - no SET for 6 weeks (control condition)

## 2. GENERAL STATISTICAL CONSIDERATIONS

### **Patient Accountability & Compliance**

A flowchart (CONSORT Diagram) will be created to present a summary of participant status. This flowchart will list the number of patients who were randomized to each treatment strategy (A, B, C, D). Then, within each group, it will list the numbers of patients who completed the study, withdrew consent, and lost to follow up.

### **Treatment Group Comparability**

Summary statistics of baseline variables (e.g. demographics, age at stroke onset, aphasia type, WAB-R AQ, all baseline assessments) will be compared by treatment groups. Dichotomous variables will be summarized as number (%). Percentages will be calculated based on the number of participants with available data for that variable. Continuous variables will be summarized by the mean and standard deviation (SD). Ordinal data will be presented as median (IQR).

### **Preliminary Analysis**

For all continuous variables, outliers will be explored. Extreme outliers will be queried to confirm that they are not erroneous before the data is locked for analysis, but outliers will not be removed from the analysis.

### **General Approach**

In general, descriptive statistics will be presented by treatment group without p-values. Dichotomous variables will be summarized as number (%). Percentages will be calculated based on the number of participants with available data for that variable. Continuous variables will be summarized by the mean and standard deviation (SD). Ordinal data will be presented as median (IQR).

## 3. PRIMARY HYPOTHESES

- Primary Endpoint:  
VPM at 3 months post treatment

We hypothesize that, compared to patients who receive control, patients who receive SET for 3, 4.5, or 6 weeks for aphasia have improved VPM at 3 months and that there is an optimal duration of SET therapy. However, this study was not designed to formally test SET versus control. This study represents the first step in a series of studies which will ultimately test this hypothesis. However, for this study no formal hypothesis tests are planned. The primary analyses will be descriptive statistics of VPM at 3 months and will estimate the effect size of SET versus control adjusting for baseline.

#### **4. SAMPLE SIZE CONSIDERATIONS**

##### *Sample Size Considerations for Comparison with Control group*

This study is not powered to detect statistically significant differences between the chosen SET dose and the control group. This will be the focus of a later and dedicated comparison study once the best dose has been defined. The sample size was determined by administrative reasons.

##### *Sample Size Considerations for Effect Size of SET versus Control group*

For each treatment group versus control we will estimate the standardized mean difference (effect size). The criteria needed to accept any duration is that the effect size is at least 0.36 (a “small” effect size). The rationale for this criteria is that if the pooled standard deviation estimate is large, because of the small sample size, then the effect size may be smaller than expected. We consider a 20% improvement from control to be the MCID. This corresponds to a 1 point improvement in VPM (5x20%=1). Given the MCID=1 and the common SD of change in VPM estimate from pilot data of 2, we expect the effect size to be  $\frac{1}{2}=0.5$ . However, with  $n=20$  per group, observed SD may be as large as 2.74 (i.e. a one-sided upper 95% confidence interval for  $SD=2$  is 2.74), thus the observed effect size may be only  $1/2.74=0.36$ .

#### **5. POPULATIONS FOR ANALYSES**

The analyses will be analyzed under the intent-to-treat principle (ITT). Under this principle, the evaluable sample will include all participants who are randomized.

#### **6. RANDOMIZATION**

A “Real-Time” randomization procedure will be implemented via the trial website on the WebDCU™ System (Data Coordination Unit, located at MUSC). Using the WebDCU™, the local site’s study staff will enter baseline and eligibility information for each subject prior to enrollment. If a subject’s eligibility status is confirmed, WebDCU™ will make the treatment assignment based on the current status of treatment group distribution at each site, age group ( $\leq 70$ ,  $>70$  years), and aphasia severity (mild/moderate, severe), as well as the overall balance of treatment assignments. A hierarchical restrictive covariate adaptive randomization procedure will be used to ensure that treatment groups are balanced within site and baseline covariates. This approach is similar to the commonly used minimization but reduces the proportion of deterministic assignments and provides a higher level of allocation randomness.

## 7. ANALYSIS OF THE PRIMARY ENDPOINT

The primary outcome is VPM which is a continuous value greater than 0. It is collected at baseline and after 3 months post treatment. The primary analysis will calculate the change in average VPM (from the Narrative Story Telling Task and Procedural Story Telling Task) from baseline. The statistical model will be a repeated measures model (SAS® MIXED procedure with REPEATED subcommand). The model will include the following fixed effects: categorical visit (1 week, 3, and 6 months post treatment period) by treatment group (class variable) interaction, site, baseline aphasia severity score (centrally scored), baseline VPM and age. The estimated difference (95% confidence intervals) in change between each SET duration group and control group will be reported. The standardized mean difference for each SET duration versus control will be used to select the best dose of SET. Since this study is not powered for direct comparison with control, no p-values will be reported.

Empirical robust sandwich estimators will be used to account for the randomization procedure in order to appropriately estimate the marginal treatment effect. The unstructured covariance matrix for repeated observations within subjects will be used. In case the model will not converge, the maximum-likelihood (ML) estimation method will be used instead of the default restricted ML (REML). If the model still does not converge, a simpler covariance structures with less parameters will be used, according to the following order: heterogeneous autoregressive(1) (ARH(1)), heterogeneous compound symmetry (CSH), autoregressive(1) (AR(1)), and compound symmetry (CS). The estimated means at the 3 month post visit of the change from baseline in VPM will be compared for the SET 3 week group versus control, SET 4.5 week versus control, SET 6 week versus control, and the combined SET durations versus control. The SAS code for this analysis is as follows:

```
PROC MIXED EMPIRICAL;
  CLASS SUBJID ARM VISIT CENTER;
  MODEL CHANGE=ARM|VISIT CENTER BASE_WABAQ BASE_VPM AGE;
  REPEATED VISITNUM / TYPE=UN SUBJECT=SUBJID R RCORR;
  LSMEANS ARM*VISIT/ cl;
RUN;
```

The adjusted means and 95% confidence intervals for each follow-up assessment visit and treatment arm will be plotted. The primary time point of interest is the 3 months post, but the 1 week and 6 month assessments will be explored to assess whether benefits are sustained over time. As an exploratory analysis, the combined SET duration versus control comparison will be tested at a two-sided alpha of 0.05.

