#### 9.2.2 Sample Size Considerations for Effect Size of SET versus Control group

For each treatment group versus control, we will estimate the standardized mean difference (effect size). The criterion needed to accept any duration is that the effect size is at least 0.36 (a "small" effect size). The rationale for this criterion is that if the pooled standard deviation estimate is large, because of the small sample size, then the effect size may be smaller than expected. We consider a 20% improvement from control to be the the minimum clinically important difference (MCID). This corresponds to an increase of 1 VPM based on our pilot data (20% of 5 VPM). Given the MCID and the common SD of change in the VPM estimate from pilot data (SD=2), the expected effect size is 0.5. However, with n=20 per group, the observed SD may be as large as 2.74 based on the one-sided upper 95% confidence interval for the common SD; thus, the observed effect size may be only 0.36.

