#### 9.4.2 Analysis of the Primary Endpoint

The primary outcome is VPM, which is a continuous value greater than 0. It is collected at baseline, 1 week, 3, and 6 months post treatment period. The primary analysis will calculate the change from baseline. The statistical model will be a repeated measures model (SAS\* MIXED procedure with REPEATED subcommand). The model will include the following fixed effects: categorical visit (1 week, 3, and 6 months post treatment period) by treatment group (class variable) interaction, site, baseline aphasia severity score, baseline VPM and age. The estimated difference (95% confidence intervals) in change between each SET duration group and control

group will be reported as the primary analysis. The standardized mean difference for each SET duration versus control will also be reported and will be used to select the best dose of SET. Since this study is not powered for direct comparison with control, no p-values will be reported. Estimates of the change at 1-week and 6 months obtained from this model are exploratory analyses. Additionally, as an exploratory analysis, the combined SET duration versus control comparison will be tested at a two-sided alpha of 0.05.

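### The final 95% intervals rest on uncorrected sandwich standard errors with 20 participants per arm: they cover about 93%, and the exploratory pooled 0.05 test runs at about 7%

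*SAP*

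**What the plan says.** SAP section 7 fits a repeated measures model to change in VPM at 1 week, 3 months and 6 months. The fixed effects are "MODEL CHANGE=ARM|VISIT CENTER BASE_WABAQ BASE_VPM AGE". On covariance it says "The unstructured covariance matrix for repeated observations within subjects will be used", and on standard errors "Empirical robust sandwich estimators will be used to account for the randomization procedure in order to appropriately estimate the marginal treatment effect". The code opens with "PROC MIXED EMPIRICAL" and has no bias-correction or degrees-of-freedom option. The fallback steps (ML, then simpler covariance structures) deal only with convergence.

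Two final outputs depend on these standard errors. One is the primary result, in Protocol 9.4.2: "The estimated difference (95% confidence intervals) in change between each SET duration group and control" group. The other is exploratory, in SAP section 7: "the combined SET duration versus control comparison will be tested at a two-sided alpha of 0.05". No p-values are reported for the individual durations. Protocol 9.4.2 describes the same model but does not mention the sandwich.

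The sample is small. SAP section 1 says "We will enroll 80 patients and randomly assign them 1:1:1:1 to one of the 4 groups (A, B, C, D"), and Protocol 9.2.2 works "with n=20 per group".

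**The concern.** The classical sandwich estimates variance from raw residuals. Fitting the mean model shrinks those residuals, so with few participants per arm the variance is biased low. The estimate is also variable in itself, which lowers coverage further. The SAP does nothing about either effect.

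The reason given for the choice does not help. A sandwich clustered on participant treats participants as independent of one another. It therefore does not represent the dependence that covariate-adaptive allocation creates. Balance on site, age and severity is dealt with by putting site, WAB-R AQ and age in the model.

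Because the plan withholds p-values for each duration, readers and the planners of the later comparison study will judge precision mainly from these intervals. If the intervals are too short, precision is overstated for every duration, and the one final test with a stated alpha exceeds it. This point concerns the final analysis of all participants. Changing only the semi-annual worsening test in SAP section 12 would leave the final intervals too short.

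**Working it through.** **The plan's own figure.** The only computed design figure is the upper SD limit, and it reproduces: √(19 × 2² / χ²₀.₀₅,₁₉) = √(76 / 10.117) = 2.74, and 1/2.741 = 0.365, which the plan gives as 0.36. Neither document states a coverage figure for the intervals.

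**Inputs from the documents.** N = 80, 20 per arm, three sites, three follow-up visits, SD of change 2, REML, unstructured covariance.
- Mean parameters: 4 arms × 3 visits = 12, plus 2 for site, plus AQ, baseline VPM and age = 17.
- Parameters bearing on a between-arm contrast at one visit: 4 + 2 + 3 = 9.

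**Inputs assumed because the documents do not give them.** Within-person correlation (0.3 or 0.6), dropout (0 to 25%), covariate distributions and the reference distribution. The main reference is t with 80 − 9 = 71 df. A normal reference makes the plan look worse.

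**Approximation by hand.** Average leverage at one visit is 9/80 = 0.1125. Raw residuals therefore shrink the standard error by a factor of about √(1 − 0.1125) = 0.942, or 5.8%. The critical value t₇₁ = 1.994 acts as 1.994 × 0.942 = 1.878, and 2·P(t₇₁ > 1.878) = 6.4%. Variability of the sandwich adds to this.

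**Simulation under the null, 3-month contrasts, uncorrected sandwich.**

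| Setting | Coverage, each duration | Size, pooled test |
|---|---|---|
| Correlation 0.6, 0–10% late dropout, 5,000 trials | 93.2–93.3% | about 6.8% |
| Correlation 0.6, no dropout, 8,000 trials, t₇₁ | 93.2% | 6.6% |
| Same, normal reference | 92.7% | 7.1% |
| All scenarios (correlation, 0–25% dropout, skewed errors, unequal arm SDs, minimization), t with N − 9 df | 93.0–93.6% | 6.5–7.3% |
| All scenarios, normal reference | 92.6–93.1% | 6.9–7.7% |
| Smaller run, equal SDs, 1,500–2,500 trials, t with N − 9 df | 93–94% | 5.5–6.4% |
| One visit, complete data, 20,000 trials, t₇₁ | 92.9% | 7.5% |

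The Monte Carlo standard error is about 0.3 to 0.5 points in the second to fifth rows. For the smaller run it is about 0.50 to 0.65 points, from √(0.068 × 0.932 / n). In the 8,000-trial base case the mean sandwich SE was 0.606 against 0.639 model-based, a ratio of 0.948.

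**Does the sandwich handle the allocation?** Minimization on site, age group and severity was simulated (6,000 trials, t₇₁). The uncorrected sandwich gave 6.5% pairwise non-coverage and a pooled size of 6.8%. Step effects at the age and severity cut-points, left out of the model, gave 6.4% and 6.8%. Model-based errors in the same two runs gave 4.8–4.9% and 4.7–4.8%. The sandwich therefore did not repair an allocation problem here.

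**Alternatives.**

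| Variance | Coverage, each duration | Size, pooled test |
|---|---|---|
| Corrected, FIRORES (Mancl–DeRouen), all scenarios | 95.4–96.0% | 4.1–5.1% |
| Corrected, ROOT (Kauermann–Carroll), 5,000-trial setting | 94.4–94.6% | not tabulated |
| Model-based, equal arm SDs | 94.8–95.3% | 4.7–5.3% |
| Model-based, unequal arm SDs | 92.5–96.5% | 2.1–9.4% |

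With arm SDs of 1.5, 2, 2.5 and 3 (3,000 trials), coverage was 93.5% for the classical sandwich, 94.9% for ROOT and 96.0% for FIRORES.

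**The case against.** The strongest reply is that nothing is decided on these standard errors. A duration is chosen on the standardized mean difference, the 0.36 threshold and 80% tolerability, and this SE enters none of them. Both documents disclaim formal hypothesis testing, and the pooled test is labelled exploratory. The shortfall is also small: half-widths of 1.994 × 0.606 = 1.21 and 1.994 × 0.639 = 1.27 VPM differ by 0.07, against a minimum important difference of 1 VPM. All of that stands, and it limits the severity. It does not make an interval that covers 93% a 95% interval.

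A second reply is that a robust variance is a sensible hedge. Allocation uses age and severity cut at thresholds (Protocol 6.2.1), while the model uses age and a centrally scored AQ. Model-based errors also fail when arm SDs differ. This is a fair reason to keep a robust variance, but not to leave it uncorrected. It is also a different reason from the one the SAP gives.

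Third, the intervals are not the only information on variability, since SAP section 15 adds unadjusted summaries and SAP section 2 supplies SDs. They remain the only planned interval statement for the adjusted duration-versus-control differences.

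Lastly, SAP sections 11 and 15 do not name the sandwich. Section 11 says only that its endpoints are analysed similarly to the primary, so the problem reaches those models only if the option is carried over.

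**Conclusion.** The concern holds. As written, SAP section 7 gives intervals that cover about 93% (92.6 to 93.6% across the scenarios, depending on the reference distribution). It also gives a pooled test with true size of about 7% (6.5 to 7.7% on the same basis; the smaller run gave 5.5 to 6.4%). These are simulation results under assumed correlation, dropout and covariate distributions. They changed little across those assumptions, and the leverage calculation predicts them from the design alone. The nearest-neighbour single imputation in SAP section 8 was not simulated; it would tend to shorten the intervals further. The change should be made, but it is not critical: estimates and the choice of duration are unaffected.

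**What to change.** In SAP section 7, fit the same fixed effects and unstructured covariance in PROC GLIMMIX with EMPIRICAL=FIRORES or EMPIRICAL=ROOT, and name one of the two in advance. FIRORES was the option checked across all scenarios and is slightly conservative. ROOT was closer to nominal and widens the intervals less. State the between-subject degrees of freedom explicitly (participants analysed minus 9). Simply removing EMPIRICAL is not equivalent, because model-based errors are unreliable when arm SDs differ.

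Apply this to the three SET–control differences and the pooled contrast, and state the estimator in SAP sections 11 and 15. SAP section 12 refits the primary model, so say whether the correction applies there too. Delete the sentence saying the sandwich accounts for the randomization procedure; if a reason is wanted, give robustness to unequal arm variances and covariance misspecification. The new code should also request the contrasts, because the printed LSMEANS statement yields only arm-by-visit means. It should use one visit variable throughout, because the REPEATED statement names VISITNUM while CLASS and MODEL use VISIT.

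The cost is SAP wording and one procedure change. Intervals become about 5% (ROOT) to 11% (FIRORES) wider than the uncorrected ones. No new data are needed.
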